ROCSS: Reinforcement of Closure of Stoma Site

A randomised controlled trial of reinforcement of closure of stoma site using a biological mesh

A randomised controlled trial from the West Midlands Research Collaborative

Protocol v8.0

12th January 2021

Protocol Summary

The ROCSS Trial was completed with 2 year follow up and published in The Lancet in 2020. A short summary is below:

Methods

ROCSS took place in 37 hospitals across three European countries (35 UK, one Denmark, one Netherlands), patients aged 18 years or older undergoing elective ileostomy or colostomy closure were randomly assigned using a computer-based algorithm in a 1:1 ratio to either biological mesh reinforcement or closure with sutures alone (control). Training in the novel technique was standardised across hospitals. Patients and outcome assessors were masked to treatment allocation. The primary outcome measure was occurrence of clinically detectable hernia 2 years after randomisation (intention to treat). A sample size of 790 patients was required to identify a 40% reduction (25% to 15%), with 90% power (15% drop-out rate).

Findings

Between Nov 28, 2012, and Nov 11, 2015, of 1286 screened patients, 790 were randomly assigned. 394 (50%) patients were randomly assigned to mesh closure and 396 (50%) to standard closure. In the mesh group, 373 (95%) of 394 patients successfully received mesh and in the control group, three patients received mesh. The clinically detectable hernia rate, the primary outcome, at 2 years was 12% (39 of 323) in the mesh group and 20% (64 of 327) in the control group (adjusted relative risk [RR] 0.62, 95% CI 0.43–0.90; p=0.012). In 455 patients for whom 1 year postoperative CT scans were available, there was a lower radiologically defined hernia rate in mesh versus control groups (20 [9%] of 229 vs 47 [21%] of 226, adjusted RR 0.42, 95% CI 0.26–0.69; p<0.001). There was also a reduction in symptomatic hernia (16%, 52 of 329 vs 19%, 64 of 331; adjusted relative risk 0.83, 0.60–1.16; p=0.29) and surgical reintervention (12%, 42 of 344 vs 16%, 54 of 346: adjusted relative risk 0.78, 0.54–1.13; p=0.19) at 2 years, but this result did not reach statistical significance. No significant differences were seen in wound infection rate, seroma rate, quality of life, pain scores, or serious adverse events.

Interpretation

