19.4. Outcome measures

Primary:

Quality of life at 5 to 8 years following closure of stoma site comparing participants who had mesh reinforcement of their abdominal wall with participants that had a standard closure. This will be assessed using the HerQLes tool^{17,18}.

Secondary: (all at 5-8 years follow-up)

- Participant reported incisional hernia rate
- Number of hospital visits for any hernia related reason
- Number of interventional procedures related to the stoma closure site or hernia
- Longitudinal QoL assessed using EQ-5D
- Cost analysis for all additional hernia related events

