19.7. Choice of QoL measures

A hernia-related quality of life measure will be included to provide more hernia specific information that will allow a better measure of the impact both to the patient and also to inform the cost-effectiveness analysis. The HerQLes tool was specifically designed to evaluate QoL in patients undergoing abdominal wall repair^{17,18}, such as a stoma closure. It contains 12 items, and can be used

both before and after surgery, focusing on abdominal wall function. Each of the 12 questions relate to the patient's abdominal wall function which means that it will be relevant to patients with and without a hernia (such as the ROCSS participant population). It will therefore be possible to use the same tool in both groups i.e. those who had mesh at the time of stoma closure and those who did not, and for participants with and without a hernia.

The HerQLes quality of life survey was not available when ROCSS was developed and so was not used for the original trial. Therefore, we do not have before and after scores to compare. However, the scores can be compared across groups of participants and it is known (from the original ROCSS data and our follow-up data) whether participants have had mesh inserted at the time of stoma closure and whether or not they have or have had a hernia. These groups will provide us with various comparisons to make and so the following exploratory analyses will be investigated limited to the primary outcome;

- Comparison within the control group (no mesh) for those who have developed a clinical or radiological hernia during the follow up period to those without a hernia. This will show the effect that having an incisional hernia has on a participant's quality of life.
- Comparison between the control group and the mesh group for those who did not develop a clinical or radiological hernia during the follow up period. This will show us if inserting a mesh in itself has any effect on quality of life. This has become an even more important comparison with the recent concern regarding mesh use.
- Comparison between the control group and the mesh group for those who have gone onto develop a clinical or radiological hernia. This will show us if developing a hernia despite having a prophylactic mesh inserted has a different effect on quality of life.

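### Mesh-versus-control HerQLes comparisons within hernia-defined subsets (19.7) condition on an outcome that mesh changes, so the conclusions stated for them do not follow

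*Protocol*

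**What the plan says.** Protocol 19.7 introduces three comparisons with the words "the following exploratory analyses will be investigated limited to the primary outcome". The primary outcome is the HerQLes score. Two of the three set mesh against control within a group defined by hernia status:

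- Hernia-free: "Comparison between the control group and the mesh group for those who did not develop a clinical or radiological hernia during the follow up period". The stated conclusion is "This will show us if inserting a mesh in itself has any effect on quality of life". The section adds that recent concern about mesh makes this comparison more important.
- Hernia: "Comparison between the control group and the mesh group for those who have gone onto develop a clinical or radiological hernia". The stated conclusion is "This will show us if developing a hernia despite having a prophylactic mesh inserted has a different effect on quality of life".

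The section attaches no assumption, adjustment or caution to either conclusion. It also notes that no HerQLes scores exist from the original trial.

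The Findings paragraph of the Protocol Summary reports that the clinical hernia rate at 2 years "was 12% (39 of 323) in the mesh group and 20% (64 of 327) in the control group". On the 1-year CT it was 20 of 229 with mesh and 47 of 226 with control.

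**The concern.** Randomisation balances the two arms as a whole. It does not balance parts of the arms selected on something that happens later and that treatment alters. Some hernia-free mesh participants are hernia-free because of the mesh. Their equivalents in the control arm have a hernia and so fall in the other subset. If the features that lead to a hernia also affect abdominal-wall quality of life, the two arms differ within each subset even when mesh does nothing to quality of life. HerQLes measures abdominal-wall function, so shared causes are plausible, and there is no baseline HerQLes score to adjust for.

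At stake is what the extended follow-up may conclude about a mesh left in place, a question that the protocol itself singles out as important. A difference in the hernia-free subset, in either direction, could be reported as an effect of the mesh when the design does not identify one.

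**Working it through.** **1. The plan's own figures (19.11 and Findings).** Analysable number: 692 × 0.85 = 588 (293 mesh, 295 control). Power = Φ(δ/√(1/293 + 1/295) − 1.96), where the root is 0.0825.

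- δ = 0.25 SD: Φ(3.03 − 1.96) = 85.8%; stated as over 85%.
- δ = 0.30 SD: Φ(3.64 − 1.96) = 95.3%; stated as over 95%.

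Crude relative risks: (39/323)/(64/327) = 0.617 and (20/229)/(47/226) = 0.420, against stated adjusted values of 0.62 and 0.42. All reproduce. These power figures apply to the full comparison, which is not in question.

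**2. Does allocation change the grouping variable?** Let pM and pC be the hernia risks with mesh and control.

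- Clinical, 2 years: pM = 0.1207, pC = 0.1957, difference 0.0750.
- CT, 1 year: pM = 0.0873, pC = 0.2080, difference 0.1206.

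It does, on the protocol's own results.

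**3. How many participants lack a counterpart?** Assume that mesh never causes a hernia. The protected share, those with a hernia under control but not under mesh, is pC − pM. Assume also that the earlier rates carry over to 5-8 years.

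| | Clinical rates | CT rates |
|---|---|---|
| Share of hernia-free mesh participants, (pC − pM)/(1 − pM) | 0.0750/0.8793 = 8.5% | 0.1206/0.9127 = 13.2% |
| Share of control participants with a hernia, (pC − pM)/pC | 0.0750/0.1957 = 38% | 0.1206/0.2080 = 58% |

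**4. How large could the bias be?** This needs a model that the documents do not supply. Assume a standard normal hernia liability L, a hernia when L exceeds a threshold c with Φ(−c) = p, a threshold that mesh raises, no effect of mesh on HerQLes, and correlation −r between L and HerQLes. Writing φ for the normal density, mean liability is φ(c)/p among those with a hernia and −φ(c)/(1 − p) among those without. The spurious mesh-minus-control difference in SD units is −r times the difference in mean liability.

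| | Clinical rates | CT rates |
|---|---|---|
| Thresholds, mesh and control | 1.171, 0.857 | 1.357, 0.814 |
| Mean liability, hernia subset | 1.664 − 1.412 = 0.252 | 1.818 − 1.378 = 0.440 |
| Mean liability, hernia-free subset | −0.229 + 0.344 = 0.115 | −0.174 + 0.362 = 0.188 |
| Bias, hernia-free, r = 0.075 to 0.50 | −0.009 to −0.058 | −0.014 to −0.094 |
| Bias, hernia, r = 0.075 to 0.50 | −0.019 to −0.126 | −0.033 to −0.220 |

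The low end of r represents a frailty that correlates 0.3 with liability and 0.25 with HerQLes (0.3 × 0.25 = 0.075). The high end correlates the whole liability with HerQLes at 0.50. Simulations of the same structure (4 million draws per scenario) agree with these values and give 0.00 SD for the comparison of all participants.

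**5. What would that do to a test in the hernia-free subset?** At clinical rates the subset is about 293 × 0.8793 = 258 v 295 × 0.8043 = 237, so the standard error is √(1/258 + 1/237) = 0.090 SD. The chance of a significant result against mesh, Φ(bias/0.090 − 1.96), is 3% for a bias of 0.01 SD, 12% for 0.07 SD and 18% for 0.094 SD. The nominal value is 2.5%.

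**The case against.** The comparisons are labelled exploratory. No power claim, decision rule or cost-effectiveness result rests on them, and 19.11 analyses all participants by intention to treat. That limits the weight of the point, and it stands. It does not rescue the wording: the label speaks to strength of evidence, not to whether a contrast estimates what is claimed for it. For subgroups defined by the minimisation factors, section 13.2 promises an interaction test, cautious interpretation and hypothesis-generating status. Section 19.7 offers nothing similar for these weaker, post-randomisation subsets.

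Four stronger readings are tempting, and the documents do not support them.

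- That the trial will produce a false signal of harm from mesh. The negative sign in step 4 comes from assuming that weaker abdominal walls go with worse scores and that mesh shifts a common threshold. Ascertainment could change it. The CT result is reported "In 455 patients for whom 1 year postoperative CT scans were available", out of 790 randomised, and the extended follow-up uses records and telephone interview (19.10) with no protocol examination or scan. Undetected hernias among apparently hernia-free controls would pull the other way. Ascertainment is not absent, however, since 19.7 draws on original and follow-up data.
- That the hernia subset is known to be too small. Sizes taken from the 2-year clinical counts do not describe the planned subset, which is clinical or radiological over follow-up. That combined count is not given, and the protocol claims no power there.
- That the arms will be grouped by mesh received. Section 19.4 does speak of "comparing participants who had mesh reinforcement of their abdominal wall with participants that had a standard closure", but 19.11 commits primary and secondary outcomes to intention to treat. The 394 − 373 = 21 mesh-arm patients without mesh belong to the original trial. Those whose stoma was not reversed are excluded from the extension (19.5), so 21 is not shown to apply.
- That both subset comparisons are said to isolate the mesh. Only the hernia-free one is. The other carries a different conclusion, with the same flaw.

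**Conclusion.** The point holds as a fault in the stated conclusions of 19.7 and should be fixed. That the subsets are not randomised groups follows from the protocol's own results and needs no model. The counterpart shares (8.5% to 13% and 38% to 58%) need one assumption about mesh and the carrying-over of earlier rates. The bias range (about -0.01 to -0.09 SD hernia-free, -0.02 to -0.22 SD with a hernia) depends wholly on assumed correlations and could change in size or sign with incomplete detection of hernias. In the hernia-free subset it is modest beside the 0.25 SD used for power. A reader might infer that the extended follow-up as a whole is compromised; it is not, because the primary intention-to-treat comparison does not condition on hernia status.

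**What to change.** In 19.7, replace the conclusions attached to the two mesh-versus-control subset comparisons with a statement that they are descriptive and non-randomised. They should be reported as an estimate with confidence interval, by allocated arm, and adjusted for baseline variables already collected under sections 7.4 and 9: for example stoma type, incision, BMI, diabetes, steroid use, parastomal and midline hernia, and baseline EQ-5D and pain. Add that only the intention-to-treat comparison of all participants estimates the effect of mesh on quality of life. Adjustment reduces imbalance on these measured factors but does not restore randomisation, so the descriptive wording is needed either way.

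A principal-stratum sensitivity analysis, for participants who would be hernia-free under either arm, is optional and belongs in the statistical analysis plan.

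The cost is a short wording change, a small amount of extra analysis and weaker stated conclusions. No new data are needed.

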19.8. Consent

The consent obtained for the original ROCSS trial does not specifically include contact to complete longer-term follow-up. Therefore, participants will be contracted by letter to inform them about ROCSS-EX. Re-confirmation of consent and agreement to continue participation will be obtained during the telephone consultation and documented in the participant's medical records (electronic or paper).

19.8.1. Contacting participants

Each site holds an identification log in the local site file that lists the participants recruited to the original ROCSS trial. This information will also be available to sites within the ROCSS-EX database, limited to only participants from the site and that are eligible for follow-up within ROCSS-EX. Sites will then establish whether each participant is alive according to the hospital records.

Prior to contacting living participants by telephone, the site will send them the ROCSS-EX Participant letter, which briefly explains;

- the nature and purpose of the follow-up
- the local team will contact the participant by telephone at least two weeks later to undertake the follow-up, or arrange a time that is convenient for them to complete it
- how they can indicate they do wish to opt out of the additional follow-up by telephone; telling the local team member when they call, or contacting the local team beforehand by either post, telephone or email, or the Trial office at BCTU by email

A Participant Information Sheet specific to ROCSS-EX that provides more detailed information and explanation will be sent with the letter.

19.8.2. Uncontactable patients

For participants that have died or otherwise cannot be contacted, data will be collected from the medical records where consent was given as part of the original ROCSS trial to the use of routinely collected data for long-term follow-up.

19.9. Blinding

Local teams at site will remain unaware of the treatment allocations participants received (blinded).

In ROCSS, participants were also blind to the treatment allocation. For either clinical reasons or at a participant's request approximately 100 participants been informed of the allocation received (unblinded). The ROCSS-EX Participant Information Sheet explains to participants the importance on maintaining blinding of staff at sites. Site staff will be asked to confirm if they are blind to the allocation when follow-up data is collected. It is possible that unblinding of site staff may be unavoidable in some instances – the allocation may be recorded in the medical records so the review cannot be completed without unintentionally unblinding the reviewer, or a participant may mention it during the telephone consultation. Site staff will be asked to confirm whether they are blind to the allocation, and if not to account for this.

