19.10. Data Collection

ROCSS-EX will collect data from trial entry into the original ROCSS trial until the date the ROCSS-EX follow-up is completed.

Data will be collected from two sources:

- The first is routinely collected electronic health records (or paper records if electronic records are unavailable) that local collaborators will access. This will include the number of hospital admissions related to either the stoma site or abdominal symptoms, the number of interventions in relation to symptoms and pathology at the stoma closure site.
- The second source of data will be the participant. Telephone interviews will collect participant reported information including the use the EQ-5D-5L and HerQLes tool. A standardised telephone script has been developed for collaborators to use during the telephone call.

The data gathered will be uploaded directly into a secure ROCSS-EX REDCap database hosted at the University of Birmingham by the local team. Worksheets to aid the collation may be used prior to upload. All local collaborators will receive trial specific training that will include the delivery of the telephone follow-up.

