19.10.2. Source Data

Source data is defined as all information in original records and certified copies of original records of clinical findings, observations, or other activities in a clinical trial necessary for the reconstruction and evaluation of the trial. In order to allow for the accurate reconstruction of the trial and clinical management of the subject, source data will be accessible and maintained.

Data	Source
Participant Reported Outcomes (EQ-5D-5L and HerQLes)	The interview administration EQ-5D-5L and HerQLes is the source, obtained by interview directly with the participant for transcription onto the CRF, in which case the CRF is source data.
Clinical event data	The original clinical annotation is the source document. This may be found on clinical correspondence, or electronic or paper participant records. Clinical events reported by the participant, either in or out of clinic (e.g. phone calls), must be documented in the source documents. Information will be transcribed onto CRFs.
Health Economics data	Obtained by (1) interview directly with the participant for transcription onto the CRF in which case the CRF is source data. (2) To the medical record in which case the original clinical annotation is the source document. Information will be transcribed onto CRFs.
Drop out	Where a participant expresses a wish to withdraw, the conversation must be recorded in the medical records.

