19.13. Team Structure

ROCSS-EX will have a central Trial Management Group to oversee the delivery of the trial. Each site will have a consultant surgeon PI and at least one local collaborator. This collaborator may be a junior doctor, nurse, or physician assistant. The local collaborators will interrogate local systems to collate routinely collected data on patient interactions with secondary care relating to the stoma site. They will also contact each alive participant to arrange and then complete telephone follow-up.

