- 7. Patients will have their follow up CT scan between 9-15 months from the date of randomisation. This will be sent electronically to the central office, or via a hard-copy CD to the Birmingham Clinical Trials Unit. Two blinded radiologists will review the scans and complete the **radiology assessment form**.
- 8. Patients will be telephoned between 21-23 months post-randomisation to remind them about the upcoming appointment at 24 months.
- 9. A fourth and final clinical follow-up will be undertaken at 2 years from randomisation. A 24 month clinical follow-up form will be completed will be completed. As a backup, a telephone questionnaire will be undertaken in the event that the follow-up appointment is delayed beyond that time frame. Patients will complete Cost Collection, Eurogol EQ-5D and VAS questionnaires.
- 10. ROCSS-EX: Extension of follow-up

Follow-up will be undertaken at 5-8 years from randomisation. A ROCSS-EX clinical follow-up form will be completed using the patient's medical notes. Patient's will be sent the ROCSS-EX Patient Letter and PIS, and then contacted by telephone and the ROCSS-EX telephone follow-up completed. Telephone follow-up will include Euroqol EQ-5D, Pain VAS and HerQles questionnaires.

Patient Pathway Summary

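### ROCSS-EX lets a local collaborator who has just read the medical notes, and may have seen the allocation, conduct the HerQLes telephone interview that is the primary outcome

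*Protocol*

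**What the plan says.** All references are to the Protocol.

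- **Primary outcome (section 19.4).** Quality of life at 5 to 8 years: "This will be assessed using the HerQLes tool".
- **How it is collected (sections 19.10 and 19.10.2).** "Telephone interviews will collect participant reported information including the use the EQ-5D-5L and HerQLes tool". The scores are "obtained by interview directly with the participant for transcription onto the CRF, in which case the CRF is source data".
- **Blinding (section 19.9).** Local teams are to remain unaware of allocation. The section then allows that unblinding of site staff may sometimes be unavoidable. One stated reason is that "the allocation may be recorded in the medical records so the review cannot be completed without unintentionally unblinding the reviewer"; the other is that a participant may mention it on the telephone. Staff are asked whether they are blind and, if not, to account for it.
- **Who does what (section 19.13).** Local collaborators search hospital systems for contacts relating to the stoma site. "They will also contact each alive participant to arrange and then complete telephone follow-up". Each site needs at least one collaborator besides the consultant PI.
- **Order (Appendix A item 10).** The form completed from the notes is mentioned first. Participants are then described as being "sent the ROCSS-EX Patient Letter and PIS, and then contacted by telephone", and the call includes HerQLes.
- **Before any contact (section 19.8.1).** Sites check hospital records for whether the participant is alive.

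**The concern.** HerQLes is a subjective score that a member of site staff asks for and writes down. The completed CRF is itself the source, so there is no participant-completed form to compare it with. If the interviewer knows whether mesh was implanted, expectations about mesh can affect how questions are put, how hesitant answers are prompted and how they are coded. Section 19.7 itself refers to recent concern about mesh, so such expectations are plausible, and they could run in either direction. A shift that differs between arms goes straight into the estimated mean difference. More participants would not reduce it, and no analysis can re-blind an interview already held.

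The main trial was stricter. Section 7.3 keeps anyone who randomised the patient or received the allocation out of post-operative assessment, and section 2 requires follow-up to be independent of the operating surgeon. The extension has no matching separation between the person who may learn the allocation and the person who collects the primary outcome.

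**Working it through.** **1. Reading the sections together.**

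| Question | What the protocol fixes | Where |
|---|---|---|
| Can the notes review reveal allocation? | Yes, conceded | 19.9 |
| Who reviews the notes? | Local collaborators | 19.13 |
| Who telephones? | Local collaborators | 19.13 |
| Can one person do both? | Yes; certain where a site has only one collaborator | 19.13 |
| Which comes first? | Notes form listed first; no order fixed in 19.8 to 19.10 | Appendix A item 10 |
| Who records HerQLes? | The interviewer | 19.10, 19.10.2 |
| Must the call precede the notes, or the caller differ? | No such rule | none |

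The record period starts at entry to the original trial (section 19.10), so the index operation falls inside it. HerQLes and EQ-5D-5L are answered by the participant and need nothing from the notes. Unblinding may be unavoidable for the review; its carry-over to the interview is not.

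**2. The plan's own figures (section 19.11).** 790 − 98 = 692 approachable (345 and 347). 692 × 0.85 = 588.2, that is 293 and 295. In SD units, SE = √(1/293 + 1/295) = 0.0825.

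Power ≈ Φ(δ/SE − 1.96):
- δ = 0.25: Φ(3.03 − 1.96) = 85.8% (85.7% by noncentral t); the plan says over 85%.
- δ = 0.30: Φ(3.64 − 1.96) = 95.3%; the plan says over 95%.

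Both reproduce, and this point does not affect them.

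**3. What a bias would do (illustration only).** Let f be the share of interviews held unblinded and b the shift in the between-arm contrast, in SD, for those interviews. Then bias = f × b. With no true difference, the chance of a significant result is 1 − Φ(1.96 − fb/SE) + Φ(−1.96 − fb/SE). The protocol gives neither f nor b, so every value below is assumed.

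| f | Bias for b = 0.1 to 0.3 SD | As a share of 0.25 SD | Two-sided type I error |
|---|---|---|---|
| 10% | 0.010 to 0.030 | 4% to 12% | 5.2% to 6.5% |
| 25% | 0.025 to 0.075 | 10% to 30% | 6.1% to 14.9% |
| 50% | 0.050 to 0.150 | 20% to 60% | 9.3% to 44.4% |
| 100% | 0.100 to 0.300 | 40% to 120% | 22.8% to 95.3% |

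Worked cell: f = 25%, b = 0.2 gives a bias of 0.05 SD; 0.05/0.0825 = 0.61; type I error 9.3%.

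The range runs from negligible to serious. It shows only that the answer depends on two quantities the protocol does not supply.

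**The case against.** The protocol is not silent. It discloses the risk, provides a standardised telephone script and training that covers the call (section 19.10), tells participants why site staff should stay blind, makes staff account for any unblinding (section 19.9), and answers allocation requests made during the call only after database lock (section 10.6). HerQLes answers come from the participant. All of this stands and makes a large interviewer effect less likely. None of it stops the caller from having read the notes first.

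Several stronger readings are tempting but not supported:

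- **That one named person always does both tasks.** Section 19.13 assigns them to a role. Larger sites could split them, though nothing asks them to.
- **That the notes must be read before the call.** Appendix A is a summary. Its explicit sequence wording links the letter to the call, not the notes form to either. The order is listed, not mandated.
- **That the notes nearly always reveal the allocation because 373 of 394 mesh-arm patients received mesh.** That is a figure for treatment received. It does not show how often reviewers open the operation note or what it says.
- **That the bias is some definite fraction of the 0.25 SD target.** Any such figure assumes both f and b.
- **That interviewer influence could never be examined.** Staff blinding status is recorded, so scores can be compared by it. How to do so belongs in the SAP, and its absence here is no fault.

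The roughly 100 participants already told their allocation (section 19.9) are a separate route. They are counted among all ROCSS participants, and some may be among the 98 already removed, so they are at most 100/692 = 14% of those approachable. Whether the call asks about participant knowledge cannot be judged, since the script and CRFs are not shown.

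**Conclusion.** The point holds as a gap in how the primary outcome is protected. The protocol recognises that the notes review can unblind, gives the review and the interview to one role, lists the notes first, and requires neither a call-first order nor a separate caller. HerQLes can therefore be collected by someone who has just seen the allocation, and for HerQLes this is avoidable.

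No bias has been demonstrated. Its size is f × b, and the documents give neither term. The conclusion rests on reading sections 19.9, 19.10, 19.10.2 and 19.13 with Appendix A item 10, not on a calculation. The sample size and power statements are unaffected. This is a cheap improvement worth making before data collection, because it cannot be made afterwards.

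**What to change.** In section 19.10 and Appendix A item 10, state that for participants who can be contacted:

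1. only vital status and contact details are checked before the call;
2. HerQLes and EQ-5D-5L are then completed by telephone and locked;
3. the clinical-record form is opened only after that.

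As an alternative, allow a caller who has not seen that participant's notes.

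Exempt participants who have died or cannot be contacted, so that their routine records can still be collected as sections 19.5 and 19.8.2 provide. In section 19.9, record staff blinding status separately for the call and for the notes review.

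The cost is a sentence or two in the protocol, a form-order rule in REDCap with the exemption built in, and one additional blinding item. The reordering needs no extra staff. The downside is that the interviewer cannot use the notes to prompt recall of events. A participant may still disclose the allocation during the call, and the change does nothing about participants who already know it.
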